Nivolumab has also demonstrated efficacy in lung cancer cohorts. A phase 1b trial of nivolumab was conducted in patients with various cancers, including 129 patients with NSCLC.²⁹ Most NSCLC patients had received multiple chemotherapies. The overall response rate in this group was 17%, with a median duration of response (DoR) of 74 weeks. At the highest dose, 45% of patients were still alive after 2 years.²⁹ A multiarm phase 1 trial examined the efficacy of nivolumab as a single agent or as part of combination therapy.²⁸ In the first arm, 56 chemotherapy-naïve patients were treated with nivolumab plus cisplatin/gemcitabine, cisplatin/pemetrexed, or carboplatin/paclitaxel. Response rates ranged from 33–50%, and 59–87% of the patients were still alive after 1 year. Serious adverse events (SAEs) occurred in 45% of patients. In a second arm, chemotherapy-naïve patients were treated with nivolumab monotherapy. Of these 20 patients, 71–80% were still alive after 1 year. In a third

arm, patients were treated with a combination of nivolumab and ipilimumab. Median OS in this group was 44.3 weeks. In a phase II safety trial of nivolumab (3 mg/kg every 2 weeks) for patients with refractory metastatic NSCLC, 20 (17%) of 117 patients reported grade 3-4 treatment-related adverse events (AEs), including fatigue (5/117 [4%]), pneumonitis (4/117 [3%]), and diarrhea (3/117 [3%]). Two treatment-associated deaths caused by pneumonia and ischemic stroke occurred in patients with multiple comorbidities in the setting of progressive disease. In the phase 3 CheckMate-017 trial, nivolumab improved survival compared with docetaxel in previously treated patients.^{31, 32}

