- To estimate the clinical benefit rate (CBR) of ADV/HSV-tk + Valacyclovir therapy in combination with SBRT used as a window of opportunity treatment before nivolumab in patients with metastatic squamous or non-squamous NSCLC and metastatic uveal melanoma.

Exploratory Objectives:

- To determine the abscopal effect of ADV/HSV-tk + Valacyclovir therapy in combination with SBRT. The primary criterion for abscopal effect evaluation will be computed tomography (CT)-based response assessment of a non-targeted lesion. The secondary criterion will be immune parameters including PD-1 and PD-L1 expression, immune infiltrates, and cytokine expression (IL-1, IL-2, IL-6, IL-12, IFN- γ , TNF- α , and GM-CSF).
- To measure the immune response to nivolumab in patients with squamous or non-squamous NSCLC and metastatic uveal melanoma.
- To assess the Th1 (cellular-based) response by measuring the following cytokines: IL-1, IL-2, IL-6, IL-12, IFN- γ , TNF- α , and GM-CSF.
- To measure TILs before and after ADV/HSV-tk + Valacyclovir therapy.
- To explore correlative tissue and blood-based biomarkers of treatment response including but not limited to T-cell cytokine profiles (IL-1, IL-2, IL-6, IL-12, IFN- γ , TNF- α , and GM-CSF), TILs, PD-1 and PD-L1 expression, effector and suppressor immunocyte populations.

Endpoints

Primary endpoint: The primary endpoint will be the ORR of ADV/HSV-tk + Valacyclovir therapy in combination with SBRT used as a window of opportunity treatment before nivolumab in patients with metastatic squamous or non-squamous NSCLC and metastatic uveal melanoma. Both RECIST 1.1 and modified irRC will be used to assess treatment response.

Secondary endpoints: Secondary endpoints will include a) DoR; b) OS and PFS rates; c) CBR; d) safety and toxicity (toxicity will be defined as any treatment-related death or any \geq Grade 3 toxicity excluding alopecia and constitutional symptoms as assessed by NCI CTCAE v4.03); e) immune-mediated antitumor activity (assessed by RECIST 1.1 and modified irRC); and f) correlative tissue and blood-based biomarkers of ADV/HSV-tk + Valacyclovir therapy in combination with SBRT used as a window of opportunity treatment before nivolumab.

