Tumor assessments: Tumor assessments will be performed at baseline and every eight (8) weeks thereafter until completion of the protocol-specified study treatment, and 30 days after the last dose of nivolumab. Disease status will be assessed using both RECIST 1.1 and modified irRC (assessments will be performed at specified time points). Serum alanine aminotransferase (ALT) levels will be assessed on day 1 of each cycle. The ALT level must be within the acceptable range before administering the study drug combination, and dosing will be discontinued either temporarily or permanently for any patient who has a severe cytokine reaction, elevated ALT level ($> 5 \times$ upper limit of normal [ULN]), or any other Grade 4 or greater adverse effect.

[figure not shown]
5. Study design

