ADV/HSV-tk will be administered intratumorally at 5×10^{11} virus particles on day 0. This dose is based on the toxicity results from the phase I/II study of ADV-tk gene therapy in combination with chemoradiation in patients with pancreatic adenocarcinoma.⁷⁷ If toxicity occurs, ADV/HSV-tk dose will be reduced to 5×10^9 vector particles per injection. If toxicity occurs with this dose modification, the dose will be further reduced to 5×10^6 virus particles per injection.

Delivery:

For the NSCLC cohort, the tumor will be identified by PET/CT by the radiation oncologist. The procedure will be managed under endoscopic ultrasound (EUS) guidance. In rare cases where the tumor cannot be accessed by EUS, a CT-guided injection will be performed. For the uveal melanoma cohort, the procedure will be managed under ultrasound or CT guidance. EUS will be performed with the patient under sedation. Patients will be monitored until the sedation has worn off. For CT-guided injections, local anesthesia will be used and patients will be monitored for several hours after the procedure.

Warnings and precautions:

Significant toxicity has not been observed with the administration of ADV/HSV-tk gene therapy alone or in combination with RT or chemotherapy in previous clinical trials.^{85, 88-90} Fever may occur due to the local inflammatory and immune response to ADV/HSV-tk, which will be treated with acetaminophen as necessary. If local inflammation is extensive or infection develops, Valacyclovir will be stopped and antibiotics and/or anti-inflammatory therapy will be given as appropriate. Other potential side effects of ADV/HSV-tk gene therapy include increased creatinine, increased liver enzymes (ALT, AST, alkaline phosphatase, and gamma-glutamyl transferase), increased bilirubin, cellulitis, and thrombocytopenia.

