12.4 Withdrawal of subjects from study

Subjects must be withdrawn from the trial (treatment and procedures) for the following reasons:

- Therapy will be discontinued temporarily or permanently for cytokine release syndrome.
- Therapy will be discontinued temporarily or permanently for elevated ALT ($> 5 \times$ ULN).
- Any Grade 4 or greater AE.

- Severe (Grade 3) or life-threatening (Grade 4) immune-mediated complications.
- TTP/HUS.
- Neurotoxicity (e.g., encephalopathy, seizures).
- Dose interruption that exceeds 21 days.
- Subject withdraws consent from study treatment and study procedures. A subject must be removed from the trial at his/her own request or at the request of his/her legally acceptable representative. At any time during the trial and without giving reasons, a subject may decline to participate further. The subject will not suffer any disadvantage as a result.
- Subject is lost to follow-up.
- Death.

Any subject removed from the trial will remain under medical supervision until discharge or transfer is medically acceptable. In all cases, the reason for withdrawal must be recorded in the CRF and the subject's medical records.

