14.3 Pregnancy

To ensure patient safety, each pregnancy occurring while the patient is on study treatment must be reported to the local IRB within 24 hours of learning of its occurrence. The pregnancy should be followed up to determine outcome, including spontaneous or voluntary termination, details of the birth, and the presence or absence of

any birth defects, congenital abnormalities, or maternal and/or newborn complications. The newborn will be followed for at least 12 months.

Pregnancy should be recorded on a Clinical Trial Pregnancy Form and reported by the investigator to the local IRB. Pregnancy follow-up should be recorded on the same form and should include an assessment of the possible relationship to the study treatment and any pregnancy outcome. Any SAE experienced during pregnancy must be reported on the SAE Report Form.

15 Statistical methods

15.1 Sample size.

Study Design and Sample Size Calculation: For the NSCLC cohort, a sample size of 16 patients achieves 80.3% power to detect the difference between a null hypothesis of ORR of 3% and treatment ORR of 25% (alternative hypothesis) at a 0.05 significance level (i.e., alpha) in a one-sided Fisher's exact test. For the uveal melanoma cohort, a sample size of 9 patients achieves 80.4% power to detect the difference between a null hypothesis of ORR of 3% and treatment ORR of 30% (alternative hypothesis) at a 0.05 significance level (i.e., alpha) using a one-sided Fisher's exact test. Power calculations were performed using nQuery Advisor 7.0. For both the NSCLC and uveal melanoma cohorts, an initial cohort of 3 patients will be followed for toxicity through the first cycle of nivolumab. If only 1 of 3 patients experience toxicity, then 3 more patients will be enrolled. If no more than 1 of 6 patients experience toxicity, then the trial will be fully opened. The staggering interval will be 5 weeks for the run-in cohort. Toxicity will be defined as any Grade 3 or greater toxicity excluding alopecia and constitutional symptoms as assessed by NCI CTCAE v4.03. Hematological toxicities will have a window of 21 days to resolve.

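### The run-in toxicity definition leaves out constitutional symptoms with no grade limit, so a Grade 4 event that requires withdrawal under Section 12.4 is scored as no toxicity

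*Combined protocol and SAP*

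**What the plan says.** Section 15.1 follows the first 3 patients of each cohort for toxicity through the first nivolumab cycle. One toxicity among 3 leads to 3 more patients, and the trial opens fully if at most 1 of 6 has a toxicity. The event counted is defined there: "Toxicity will be defined as any Grade 3 or greater toxicity excluding alopecia and constitutional symptoms as assessed by NCI CTCAE v4.03".

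The secondary endpoints in Section 4 use a two-part definition. The first part reads "toxicity will be defined as any treatment-related death". The second takes events at or above "Grade 3 toxicity excluding alopecia and constitutional symptoms as assessed by NCI CTCAE v4.03". The Safety Criteria in Section 7 and the text of Section 12 repeat both parts. Section 15.1 has only the second. None of the four places caps the excluded symptoms by grade or says which terms are constitutional.

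Section 12.4 opens its list with "Subjects must be withdrawn from the trial (treatment and procedures) for the following reasons", and one entry is "Any Grade 4 or greater AE". The tumor-assessment paragraph of Section 4 stops dosing, temporarily or permanently, for "any other Grade 4 or greater adverse effect". Neither place exempts constitutional symptoms.

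**The concern.** The same event gets two incompatible treatments. Section 12.4 regards a Grade 4 constitutional event as serious enough to take the patient off the trial, while Section 15.1 does not count it when deciding whether more patients should be exposed.

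The run-in is the only numeric safety rule in the documents. The stopping rules in Section 17 are qualitative, and nothing feeds an uncounted event back into the run-in tally. Because constitutional symptoms are undefined, whether a given event counts would be settled case by case, in a group of 3 or 6 patients where one reclassification can change the decision. The toxicity rate reported under the secondary endpoint carries the same gap for non-fatal events.

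**Working it through.** **The plan's own figures.** Section 15.1 computes only power. With an exact one-sided binomial rule:

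- 16 patients, success at 3 or more responses, 3% against 25%: alpha 0.0113, power 0.8029 (stated 80.3%).
- 9 patients, success at 2 or more responses, 3% against 30%: alpha 0.0282, power 0.8040 (stated 80.4%).

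Both reproduce and are unaffected by this point. The plan states no operating characteristic for the run-in.

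**The texts side by side.**

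| Place | Rule | Constitutional symptoms | Treatment-related death |
|---|---|---|---|
| 15.1, run-in | Grade 3 and above counts | excluded, no upper grade | not mentioned |
| 4 (endpoints), 7, 12 | Grade 3 and above counts | excluded, no upper grade | counted separately |
| 12.4 | withdrawal at Grade 4 and above | no exemption | death listed |
| 4 (tumor assessments) | dosing stopped at Grade 4 and above | no exemption | not mentioned |

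**Tracing a case.** Suppose two of the first three patients each have a Grade 4 constitutional event and no other event of Grade 3 or above. Under Section 12.4 both are withdrawn. Under Section 15.1 the tally is 0 of 3. The plan does not say what follows 0 of 3, but the natural reading is that the cohort opens. Had the two events counted, the tally would be 2 of 3, which meets neither the expansion condition nor the opening condition. Read literally, even a fatal constitutional event falls outside the Section 15.1 count, because the death part of the definition is missing there.

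**How large could it be?** The documents give no rate for Grade 4 constitutional events. The nearest figures are for fatigue under nivolumab alone: 4% Grade 3-4 (5 of 117) in the phase II trial described in Section 1.1, and 7% severe in Table 6. Take 0 of 3 as opening and let p be the per-patient probability of a counted event:

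P(open) = (1-p)^3 + 3p(1-p)^2 × (1-p)^3

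If all severe fatigue counted and nothing else occurred:

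- p = 0.04: 0.8847 + 0.0978 = 0.983
- p = 0.07: 0.8044 + 0.1461 = 0.950

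Counting all of it would keep a cohort from opening in 1.7% to 5.0% of run-ins. The Grade 4 part alone would be smaller.

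The effect is larger on top of other toxicity, for which the documents give no rate. As an assumption, let 10% of patients with an event of Grade 3 or above have only constitutional ones, so the counted rate is 0.9 times the true rate:

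| Assumed true rate | P(open), all counted | P(open), 10% uncounted |
|---|---|---|
| 20% | 0.709 | 0.752 |
| 30% | 0.494 | 0.557 |
| 40% | 0.309 | 0.378 |

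This table covers the whole Grade 3 and above exclusion, so it overstates the Grade 4 conflict.

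**The case against.** The best defence is that an individual withdrawal rule and a cohort gate serve different purposes and need not match. The exclusion appears in four places, so it looks deliberate. The events are not lost either: Section 15 tabulates all AEs, SAEs, discontinuations and worst grade per patient; SAEs go to the independent monitors as they occur; and the Section 17 stopping rules cover adverse effects of any kind. This defence limits the point but does not remove it. Safety reporting is complete, but the opening decision in Section 15.1 rests on the defined toxicity, not on those tables. A deliberate exclusion would still need a boundary, and the plan does not say that the two rules are meant to differ at Grade 4.

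Several stronger readings are tempting but unsupported.

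- From the 4% and 7% fatigue figures a reader might infer a 12-20% chance of at least one ignored severe event in 3 patients (1-0.96^3 = 0.115; 1-0.93^3 = 0.196) and 22-35% in 6 (0.217; 0.353). From 5 of 20 patients with Grade 3-4 events a reader might infer that 25% go uncounted. These are Grade 3-4 or ungraded severe rates over whole treatment, not Grade 4 events in the run-in. The 25% is also an upper bound, since those patients may have had other events. One event does not close the gate in any case.
- A reader might infer that the gate is blind to vector toxicity, since Section 9.1 says "Fever may occur due to the local inflammatory and immune response to ADV/HSV-tk". It gives no severe rate, and it also lists laboratory changes, cellulitis and thrombocytopenia, which are not constitutional on their face. Table 6 lists pyrexia for nivolumab too.
- Cytokine reactions might seem to be excluded. Sections 4 and 12.4 name them as events in their own right, and nothing classes them as constitutional.
- The exclusion might seem to reach fatal events everywhere. Sections 4, 7 and 12 count treatment-related death; only Section 15.1 omits it.

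**Conclusion.** The inconsistency is real and follows from the text alone: an adverse event that requires withdrawal can be scored as no toxicity in the run-in gate and in the defined toxicity rate. Its frequency cannot be derived from the documents and is probably small.

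The conclusion rests on reading the exclusion as written, without an implied grade cap, and on some constitutional term being gradable at Grade 4. The second cannot be checked here, because Appendix C only points to the CTCAE files. The probabilities also assume that 0 of 3 opens the cohort. The point is worth correcting because the gate is small, is the only numeric safety rule, and can be repaired with little text.

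**What to change.** Reconcile the toxicity definitions in Sections 4, 7, 12 and 15.1 with the adverse-event criteria of Section 12.4:

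1. Add one clause in each of the four places: the exclusion of constitutional symptoms does not apply to an adverse event that itself requires withdrawal under Section 12.4. Refer to its adverse-event criteria only, since the list also contains consent withdrawal and loss to follow-up, which are not toxicities.
2. State which terms count as constitutional and which grades remain excluded.
3. Add the treatment-related-death part to Section 15.1, so that the run-in and the endpoint use one definition.

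This changes what is counted. It leaves the dosing and withdrawal rules as they are and takes no position on them. The cost is one clause in four places plus a short list of terms. The run-in may occasionally expand or pause for a constitutional event, and the reported toxicity rate may be slightly higher. Sample size and power do not change.

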Appendix A: ECOG/Karnofsky Performance Status Criteria

ECOG Performance Status Scale		Karnofsky Performance Scale	
Grade	Descriptions	Percent	Description
0	Normal activity. Fully active, able to carry on all pre-disease performance without restriction.	100	Normal, no complaints, no evidence of disease.
		90	Able to carry on normal activity; minor signs or symptoms of disease.
1	Symptoms, but ambulatory. Restricted in physically strenuous activity, but ambulatory and able to carry out work of a light or sedentary nature (e.g., light housework, office work).	80	Normal activity with effort; some signs or symptoms of disease.
		70	Cares for self, unable to carry on normal activity or to do active work.
2	In bed < 50% of the time. Ambulatory and capable of all self-care, but unable to carry out any work activities. Up and about more than 50% of waking hours.	60	Requires occasional assistance, but is able to care for most of his/her needs.
		50	Requires considerable assistance and frequent medical care.
3	In bed > 50% of the time. Capable of only limited self-care, confined to bed or chair more than 50% of waking hours.	40	Disabled, requires special care and assistance
		30	Severely disabled, hospitalization indicated. Death no imminent.
4	100% bedridden. Completely disabled. Cannot carry on any self-care. Totally confined to bed or chair.	20	Very sick, hospitalization indicated. Death not imminent.
		10	Moribund, fatal processes progressing rapidly.
5	Dead	0	Dead

Appendix B: New York Heart Association Classifications

Class	Description
I	Patients with cardiac disease but without resulting limitations of physical activity. Ordinary physical activity does not cause undue fatigue, palpitation, dyspnea, or anginal pain.
II	Patients with cardiac disease resulting in slight limitation of physical activity. They are comfortable at rest. Ordinary physical activity results in fatigue, palpitation, dyspnea, or anginal pain.
III	Patients with cardiac disease resulting in marked limitation of physical activity. They are comfortable at rest. Less than ordinary physical activity causes fatigue, palpitation, dyspnea, or anginal pain.
IV	Patients with cardiac disease resulting in inability to carry on physical activity without discomfort. Symptoms of cardiac insufficiency or of the anginal syndrome may be present even at rest. If any physical activity is undertaken, discomfort is increased.

This table is an excerpt from the Oxford Textbook of Medicine, 2nd ed. Oxford; New York: Oxford University Press, 1987, p. 2228.

Appendix C: Version 4.03 (dated June-14-2010)

CTCAE Files

NCI Common Terminology Criteria for Adverse Events (CTCAE) v.4.03 data files and related documents are published here. The most current release files appear in this directory:

Files: Booklet

[CTCAE 4.03 2010-06-14 QuickReference 5x7.pdf](#)

Content

Most recent release of core terminology: PDF document, traditional small booklet format.

<http://evs.nci.nih.gov/ftp1/CTCAE/About.html>

Appendix D: Modified irRC, derived from RECIST 1.1

Overall responses derived from changes in index, non-index, and new lesions

Measurable Response	Non-Measurable Response		Overall Response Using Modified irRC
Index and New, Measurable Lesions (Tumor Burden)	Non-Index Lesions	New, Non-Measurable Lesions	
Decrease 100%	Absent	Absent	irCR*
Decrease 100%	Stable	Any	irPR*
Decrease 100%	Unequivocal progression	Any	irPR*
Decrease \geq 30%	Absent / Stable	Any	irPR*
Decrease \geq 30%	Unequivocal progression	Any	irPR*
Decrease < 30% to increase < 20%	Absent / Stable	Any	irSD
Decrease < 30% to increase < 20%	Unequivocal progression	Any	irSD
Increase \geq 20%	Any	Any	irPD

* Assuming that the response (irCR and irPR) and progression (irPD) are confirmed by a second, consecutive assessment at least 4 weeks apart (normally it should be done 6 weeks apart).

Key Milestones:

FPFV / First Dose:

LPLV / Last Subject completed:

Database Lock:

Final Report:

Sponsoring Department: HMHCC &HMHRI

Prepared by: _____

Date _____
